9.1.1.3. Matching process

As in prior applications of observational studies of the Pfizer-BioNTech COVID-19 using an unexposed comparator,²¹⁻²⁴ the cohort study will match exposed to unexposed individuals using a 1:1 ratio. Matching will be done with replacement, as follows.

- On the day an exposed individual receives a bivalent vaccine dose, individuals will be matched to unexposed individuals who, on that same day, have exactly the same values for the matching variables, provided that both members of the pair meet the eligibility criteria that day. If more than one unexposed individual is found to match a bivalent vaccinated individual, one will be selected at random.
- Exposed individuals will be allowed to have served as unexposed controls in prior matches, and unvaccinated individuals will be allowed to serve as controls more than once (during different time periods).

Individuals will be matched on the following variables, that have been shown to control for confounding well in prior studies:^{21,22}

- Age – 2-year age groups (consecutive years);
- Sex (male, female) – exact matching;
- Place of residence – exact matching, at the level of clinical practice, neighbourhood, or proxy as available (specific for data source);
- History of COVID-19 vaccination, containing the following categories – exact matching:
 - Never vaccinated;
 - Vaccinated with a total of i doses (where i can range from 1 to the maximum number of plausible doses at the time the matching is performed) with the last dose received in calendar month j (where j can range from the first month to the last month of the study period);
- Brand of last COVID-19 vaccine received;
- History of hospitalisation for COVID-19;
- Pregnancy status yes, no (exact matching):
 - Among pregnant women, matching will take a ‘greedy matching’ approach, in which a matched individual will be sought first by last menstrual period (LMP) within 7 days of each other; if no matches are found, the matching period will be extended to 30 days;
- Immunocompromised (yes/no) – exact matching;
- Number of pre-existing conditions considered by the Centers for Disease Control and Prevention (CDC) as risk criteria (0, 1, >1);²²
- Socioeconomic status/education level (as available, exact matching);
- This selection of matching variables is based on prior observational studies.^{22,24,25} The selection of variables will be tailored based on the availability of variables in each data source.

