The following and other variables will be considered as potential confounders in the matched cohort design and, those listed below will be used as matching variables:

- age,
- sex,
- place of residence (as available),
- prior COVID-19 vaccination history,
- history of hospitalization for COVID-19
- pregnancy status and duration of pregnancy
- immunocompromised status,
- COVID-19 disease risk criteria, as defined by the US Centers for Disease Control and Prevention,
- socioeconomic status/education level (as available).

PFIZER CONFIDENTIAL

CT24-WI-GL02-RF02 4.0 Non-Interventional Study Protocol Template For Secondary Data Collection Study

01-Jun-2022

Page 11 of 64

The list of potential confounders may be updated, based on emerging scientific evidence.

Data sources: The study will be performed within the following selected data sources: Pedianet (IT), PHARMO Institute for Drug Outcomes Research (PHARMO) (NL), the Norwegian health registers (NHR) (NO), EpiChron Research Group on Chronic Diseases at the Aragon Health Sciences Institute (EpiChron) (ES), Sistema d'Informació per el Desenvolupament de la Investigació en Atenció Primària (SIDIAP) [Information System for the Improvement of Research in Primary Care] (ES), and Clinical Practice Research Datalink (CPRD) (UK).

Study size: The sample size will be determined by the uptake of bivalent BA.1 and bivalent BA.4-5 during the study period.

Data analysis: Data from the matched cohort design will be analysed as follows:

- Conditional exchangeability: The pairs will be matched using several variables considered as potential confounders to ensure conditional exchangeability. Additional standard epidemiological methods, based on propensity scores, will be used to improve adjustment for confounding, if necessary.
- The effect estimates will be reported as risk ratios and risk differences (and their corresponding 95% CIs) for those exposed to a Pfizer-BioNTech COVID-19 bivalent vaccine compared with those not exposed to any COVID-19 vaccine during follow-up.
- Appropriate data analysis models will be used to estimate the incidence rate ratios of AESIs in the risk and the control windows in the SCRI study.

Milestones:

Milestone	Planned Date ^a
Registration in EU PAS Register	After regulatory endorsement and prior to the start of data collection
Start of data collection ^b	31 March 2024
End of data collection	30 September 2025
Interim report 1 ^c	14 May 2025
Final study report ^{c,d}	30 April 2026

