Respiratory system	Acute respiratory distress syndrome	365	Cohort
Reproductive system	Secondary amenorrhea	183	Cohort
	Hypermenorrhea	183	Cohort
Skin and mucous membrane, bone and joints	Erythema multiforme	42	Cohort
	Chilblain-like lesions	42	Cohort
Other	Anosmia, ageusia	42	Cohort
	Anaphylaxis ^a	1 ³¹	Cohort/SCRI
	Multisystem inflammatory syndrome	42	Cohort
	Death (any causes)	365	Cohort
	Subacute thyroiditis	365	Cohort
	Sudden death	365	Cohort
Pregnancy outcome, maternal	Gestational diabetes	Any time pregnancy	Sub-cohort
	Preeclampsia	After 20 weeks gestation	Sub-cohort
	Maternal death	Any time pregnancy	Sub-cohort
Pregnancy outcome, neonates. Define design taking trimester into account	Foetal growth restriction	Any time pregnancy	Sub-cohort
	Spontaneous abortions	At spontaneous abortion	Sub-cohort
	Stillbirth	At birth	Sub-cohort
	Preterm birth	At preterm birth	Sub-cohort
	Major congenital anomalies ^a	1 year after birth	Sub-cohort
	Microcephaly	At birth	Sub-cohort
	Neonatal death	At birth	Sub-cohort
Termination of pregnancy for foetal anomaly	At termination	Sub-cohort	

090177e19fa902a7Approved\Approved On: 12-Jan-2024 21:20 (GMT)

Table 1. Safety outcomes: adverse events of special interest (AESIs) with estimated risk intervals and preferred study design

Body system / classification	Adverse event of special interest	Estimated risk interval (days)*	Preferred study design*
	Small size for gestational age	Any time pregnancy	Sub-cohort
Any	Severe COVID-19 ^b	Any	Cohort

SCRI = self-controlled risk interval

* Time zero corresponds to the day of vaccination (i.e., a 42-day risk interval means that individuals are followed from the day of vaccination to day 41). Risk interval based on the ACCESS project results and other publications.

a For these AESI clinical validation will occur.

b Severe COVID-19 defined as either COVID-19 hospitalisation or death

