9.3.3.1. Demographics

- Age:
 - Age will be grouped in categories in line with published background incidence rates from ACCESS (0-17, 18-29, 30-39, 40-49, 50-59, 60-65, 66-69, 70-79, 80+ years);
 - The age group 0-17 years will be stratified as follows, where feasible: 0-1, 2-4, 5-11, 12-15, 16-17;
- Sex;
- Pregnancy status and pregnancy trimester;
- Geographic region, as appropriate in each data source;
- Socioeconomic status (including housing, employment, and income, if available);
- Date of vaccination (categorised as appropriate, eg, by year or month).

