9.7.1.6. Adjustment for baseline imbalances

Propensity score methods will be used to estimate the adjusted risks, cumulative incidences, effect estimates and their corresponding 95% CIs to account for potential baseline confounding. Specifically, the propensity score (ie, the probability of receiving bivalent BA.1 or bivalent BA.4-5 vaccine conditional on baseline covariates listed in Section 9.3.3) will be used to construct inverse probability weights.^{40,41} More details, including the variable selection and construction of weights, will be provided in the SAP. The incidence of COVID-19-related outcomes in the first few days after baseline will be evaluated as a negative control outcome for baseline exchangeability.

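### For spontaneous abortion, the 30-day LMP fallback with gestation listed only as trimester in the weighting covariates can leave residual confounding by gestation

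*Protocol*

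**What the plan says.** Protocol Section 9.1.1.3 matches pregnant women in two steps. At first, "a matched individual will be sought first by last menstrual period (LMP) within 7 days of each other"; then, "if no matches are found, the matching period will be extended to 30 days". The second step applies to every pregnancy outcome, with no exception for spontaneous abortion. Section 9.1.1.2 gives both members of a pair the same calendar date as time zero, so a 30-day gap in LMP is a 30-day gap in gestation at the start of follow-up.

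The covariate list in Section 9.3.3.1 has "Pregnancy status and pregnancy trimester" and no finer measure of gestation. Section 9.7.1.6 builds the weights from the propensity score, defined as "the probability of receiving bivalent BA.1 or bivalent BA.4-5 vaccine conditional on baseline covariates listed in" Section 9.3.3. It leaves variable selection and the construction of the weights to the SAP.

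Table 1 in Section 9.3.2 gives the risk interval for spontaneous abortion as "At spontaneous abortion", with no gestational limit for entry. Its note on this outcome group asks for a design that takes trimester into account. The abstract names "pregnancy status and duration of pregnancy" among the potential confounders and matching variables, without a width.

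**The concern.** A woman's remaining risk of spontaneous abortion runs from her gestation at time zero to the gestational limit that defines the outcome. It can only fall as gestation advances, and it may fall a good deal within one trimester. Two women matched through the fallback can therefore start follow-up with very different remaining risks. A trimester term treats them as equal if they share a trimester. A control may even be past the limit: a vaccinee at 17 weeks and a control at 21 weeks are 28 days apart and form an admissible pair. If the outcome is defined up to about 20 weeks (an assumption), that control cannot have the event.

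Gaps in both directions need not cancel. Where remaining risk falls along a convex curve, a control some weeks earlier adds more risk than a control equally later removes, so symmetric mismatch raises the controls' mean risk and the vaccine looks protective. Very early in pregnancy mostly later controls are available, and the error runs the other way. In a safety study, spurious protection could hide a harm and spurious harm could raise a false signal.

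**Working it through.** The protocol gives no figure for spontaneous abortion, so there is nothing of its own to reproduce.

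**Inputs from the protocol.** Gap limits of 7 and 30 days, 1:1 matching, a common time zero (Sections 9.1.1.2 and 9.1.1.3), and trimester as the only gestation covariate (Section 9.3.3.1).

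**Assumptions, not in the protocol.** The hazard falls exponentially from week 5 to week 20, with a half-life of 1.5 to 4 weeks. Total risk from week 5 is 10% to 15%. There is no vaccine effect. Gaps are uniform over 0 to 7 days in the first tier and 8 to 30 days in the fallback, equally often in each direction.

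**Formula.** Remaining risk at gestation g is R(g) = 1 − exp(−∫ hazard from g to week 20). The null risk ratio is mean R(exposed) / mean R(control). Any departure from 1 is due to gestation.

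**Step 1: one pair inside the first trimester.** Exposed at 6 weeks, control at 10 weeks 2 days (30 days later), total risk 15%:

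- half-life 1.5 weeks: 0.0973 / 0.0139 = 7.0
- half-life 2.5 weeks: 0.1153 / 0.0349 = 3.3
- half-life 4 weeks: 0.1259 / 0.0556 = 2.3

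Both women have the same trimester value, so trimester adjustment cannot touch this ratio.

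**Step 2: why symmetric gaps need not cancel.** Take an exposed woman at 12 weeks, half-life 2.5 weeks, total risk 15%, so R = 0.0209. Against a control 30 days earlier the ratio is 0.29, so the control's risk is 0.0209 / 0.29 = 0.0721. Against a control 30 days later it is 4.51, so the control's risk is 0.0209 / 4.51 = 0.0046. The mean control risk is (0.0721 + 0.0046) / 2 = 0.0384, and 0.0209 / 0.0384 = 0.54. One control on each side gives about 0.54, not 1.

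**Step 3: whole cohort, symmetric gaps.** Controls that would fall below week 5 are flipped to the later side. Ranges run over the assumed hazards.

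| Vaccination, uniform over | 7-day pairs only | 25% fallback | 50% fallback | 100% fallback |
|---|---|---|---|---|
| weeks 6-20 | 0.97-0.99 | 0.97-1.00 | 0.98-1.01 | 0.99-1.04 |
| weeks 8-20 | 0.96-0.99 | 0.82-0.96 | 0.71-0.94 | 0.57-0.89 |
| weeks 10-20 | 0.96-0.99 | 0.77-0.95 | 0.64-0.90 | 0.48-0.83 |
| weeks 5-10 | 1.01-1.03 | 1.07-1.14 | 1.14-1.27 | 1.31-1.64 |

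The treatment of controls below week 5 matters. If they are dropped instead, weeks 6-20 give 0.79 to 0.99 over all fallback shares. For weeks 5-10 with 25% fallback pairs, the two rules together span 1.03 to 1.14.

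**Step 4: adjustment.** Weighting controls to the exposed distribution of trimester leaves these figures essentially unchanged. Weighting by completed week returns about 1.00. The by-week weighting gives no weight to controls past week 20, because no exposed woman is there.

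**The case against.** The strongest reply is that no bias has been demonstrated. The fallback is used only after the 7-day search fails, and the protocol does not say how often that happens. If vaccination is spread evenly over weeks 6 to 20, the early and late errors largely offset and the overall null ratio is 0.97 to 1.04 under the flipping rule. The large ratios in narrow gestation bands are not planned estimates, because Section 9.3.5 treats pregnant women as one subgroup. All hazards here are assumed. This stands. A reader might infer that pairs generally differ by 30 days, that the fallback will be common, or that the risk ratio is biased by gestation; the protocol supports none of these.

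The further argument that bias needs exposed women to be systematically earlier or later than their controls does not stand. The rows for weeks 8-20 and 10-20 use gaps drawn equally often in each direction.

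The second reply is that the protocol leaves room for a finer approach. The abstract lists duration of pregnancy as a potential confounder, the covariate list is not closed, variable selection goes to the SAP, balance is checked under Section 9.7.1.2, and Table 1 marks the pregnancy design as still to be defined. This also stands in part: the SAP may already use weeks. But the only measure of gestation in the covariate list is trimester, Table 1's design note points to trimester too, and the 30-day limit is fixed in the protocol itself.

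The third reply, that a wider limit keeps pairs at some cost in bias, is fair. It is why the 30-day pairs need not be removed from the main analysis.

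**Conclusion.** The point holds as a possibility of residual confounding, not as a shown bias. For spontaneous abortion, the 30-day fallback with a trimester-only covariate can move the null risk ratio in either direction. The size depends on gestation at vaccination, the share of fallback pairs and the handling of very early controls, none of which the protocol gives. Under the stated assumptions it ranges from negligible (0.97 to 1.04, weeks 6 to 20, too-early controls flipped later) to material (0.71 to 0.94, weeks 8 to 20, half the pairs in the fallback). Adjustment by completed week removes it under those assumptions and trimester adjustment does not. The correction is worth making now because the finer variable is already needed for matching.

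**What to change.** 1. In Section 9.3.3.1, replace pregnancy trimester with gestational age at time zero in completed weeks, entered in a flexible form, for the weights in the pregnancy-outcome analyses. This costs nothing, because LMP is already used for matching.
2. For spontaneous abortion, include only pairs in which both women are, at time zero, below the gestational limit that defines the outcome, and state that limit in the outcome definition. The pairs lost are those in which at least one woman could no longer have the event.
3. Report the distribution of LMP gaps by arm, with their sign, and the share of pairs that used the fallback.
4. Add a sensitivity analysis restricted to pairs within 7 days of LMP. The cost is fewer pairs in that analysis only; the main analysis keeps the 30-day pairs.

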9.1.1.4. Follow-up

Individuals will be followed from time zero until the end of the study period (31 August 2024, or 30 June 2025 for pregnancy outcomes), the occurrence of the AESI being analysed, death, or disenrollment from the data source, whichever occurs first. Additionally, the

PFIZER CONFIDENTIAL

CT24-WI-GL02-RF02 4.0 Non-Interventional Study Protocol Template For Secondary Data Collection Study

01-Jun-2022

Page 18 of 64

matched pair will be censored when the unexposed individual of the pair receives any COVID-19 vaccine or when the exposed individual in the pair receives a non-Pfizer vaccine.

9.1.2. Self-controlled risk interval design

The SCRI design will be used as a secondary analysis to compare the occurrence of specific AESIs for which the design is recommended.²⁶ Occurrence of an AESI in a specified risk interval following a dose of bivalent BA.1 or bivalent BA.4-5 will be compared with the occurrence of the same AESI in a later interval (control interval), in the same individual. AESIs that are appropriate for this study design are those that are:

[figure not shown]
- rare, with a transient risk after exposure;
- have a constant event rate within the observation periods;
- have an occurrence that does not alter the duration of the observation window.²⁷

The SCRI design will be used to compare the risk of each AESI during a prespecified period following vaccine administration during which there is a hypothesised increased risk of the outcome ('risk period') with a self-matched control period, used to assess the baseline risk of the outcome.

The risk periods proposed for each AESI and the AESIs that will be analysed using the SCRI design are summarised in [Table 1](#).

A prespecified post-vaccination control period will be used for each outcome. The use of a control period after the risk period (rather than the use of a control period before the risk period) avoids bias from outcomes affecting the probability of exposure (eg, the outcome could be a contraindication for vaccination or could delay vaccination) (Figure 1).

Figure 1. Self-controlled risk interval design

T = time, in days.

Note: Example with a risk period of 42 days and a control period of 42 days.

9.2. Setting

9.2.1. Inclusion criteria

9.2.1.1. Cohort design

- Individuals must meet all the following criteria to be eligible for inclusion in the cohort study:
 - have a minimum of 12 months (or from birth if enrolled in the data source at birth) of continuous enrollment in the data source at time zero;
 - have complete information on the matching variables;
 - be in the population targeted by recommendations for vaccination with the bivalent BA.1 or BA.4-5 COVID-19 vaccines, either as a booster, ie, an additional dose several months or longer after the two or three-dose primary vaccine series, as per national or regional recommendations, or as primovaccination, ie, as the first ever COVID-19 vaccine received:
 - if an individual has not received any COVID-19 primovaccination, they will meet this criterion;
 - if an individual has received primovaccination, they will meet the above criterion if they:
 - meet the age threshold or other criteria for additional COVID-19 vaccine doses after primovaccination;
 - do not have any comorbidities or other characteristics for which a short interval between doses is recommended by local vaccination policies and have had prior COVID-19 vaccination at least 11 months before baseline;
 - have comorbidities or other characteristics for which a short interval between doses is recommended by local vaccination policies and have had prior COVID-19 vaccination at least 5 months before baseline.

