7. RATIONALE AND BACKGROUND

In November 2021, World Health Organization (WHO) designated the severe acute respiratory syndrome coronavirus 2 (SARS-CoV-2) variant B.1.1.529 as a variant of concern and named it Omicron.³ The Omicron variant, and its descendant sub-lineages, eg, BA.4-5, have since spread to become the dominant circulating variant worldwide.⁴ The Omicron variant has greatly increased transmissibility and immune-evasion capacity compared with prior circulating variants.⁵ In addition, there is evidence that the original mRNA vaccines provide lower protection against the Omicron variant.⁶⁻⁸

PFIZER CONFIDENTIAL

CT24-WI-GL02-RF02 4.0 Non-Interventional Study Protocol Template For Secondary Data Collection Study
 01-Jun-2022

Page 15 of 64

090177e19fa902a7Approved\Approved On: 12-Jan-2024 21:20 (GMT)

Pfizer-BioNTech has developed bivalent formulations (Comirnaty Original/Omicron BA.1 (bivalent BA.1) and Comirnaty Original/Omicron BA.4-5 (bivalent BA.4-5)) of the Coronavirus Disease 2019 (COVID-19) mRNA-based vaccine. On 01 September 2022 and 12 September 2022, bivalent BA.1 and bivalent BA.4-5, respectively, were authorised for use in the European Union as a booster following a primary vaccination series, at least 3 months after the last dose of any COVID-19 monovalent vaccine.⁹⁻¹¹ Bivalent BA.1 is authorised for individuals aged 12 years and older, while bivalent BA.4-5 is authorised for individuals aged 5 years and older.¹² On 06 December 2022, the Emergency Task Force of the European Medicines Agency (EMA) concluded that bivalent BA.4-5 may be used as a primary vaccination series in adults and children who have not been previously vaccinated against SARS-CoV-2.¹

Safety data reported from Vaccine Adverse Event Reporting System (VAERS) and v-safe in the United States up to October 2022 demonstrate a similar safety profile for the bivalent booster as that reported for the monovalent booster.¹³ However, to gain a more complete understanding, safety monitoring of the bivalent Pfizer-BioNTech COVID-19 booster vaccines is needed in European countries.

This non-interventional study is designated as a Post-Authorisation Safety Study (PASS) and is a commitment to the EMA. This study complies with the European Network of Centres for Pharmacoepidemiology and Pharmacovigilance ENCePP¹⁴ and Accelerated Development of VAccine benefit-risk Collaboration in Europe (ADVANCE)¹⁵ codes of conduct.

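### Section 9.1.1.3 limits the month of last dose to the study period, so eligible booster recipients have no printed matching category before August 2023 (11-month rule) or February 2023 (5-month rule)

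*Protocol*

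**What the plan says.** Protocol Section 9.1.1.3 pairs each bivalent recipient with an unexposed person who has identical values of the matching variables on the same day. Vaccination history is one of these variables and has two kinds of category: never vaccinated, or vaccinated with i doses, the last in calendar month j, "where j can range from the first month to the last month of the study period".

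Section 9.2.3 starts the study period at national launch of the BA.1 vaccine, September 2022 at the earliest, and ends it on 31 August 2024.

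Section 9.2.1.1 requires cohort members to "have complete information on the matching variables". It admits booster candidates "as per national or regional recommendations" and then lists three conditions for people already vaccinated:

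- A: "meet the age threshold or other criteria for additional COVID-19 vaccine doses after primovaccination".
- B: this branch covers those who "do not have any comorbidities or other characteristics for which a short interval between doses is recommended by local vaccination policies". Its gap condition is that they "have had prior COVID-19 vaccination at least 11 months before baseline".
- C: such comorbidities or characteristics are present, and the person must "have had prior COVID-19 vaccination at least 5 months before baseline".

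No connective is printed between A, B and C. Section 7 gives the authorised use "as a booster following a primary vaccination series, at least 3 months after the last dose of any COVID-19 monovalent vaccine", with primary vaccination added by the conclusion of 6 December 2022. Section 5 records that bivalent administration ended by August 2023; it is used here for that date only.

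**The concern.** The gap rules require the previous dose to lie well before the bivalent dose. The range of j requires the previous dose to lie on or after the month in which the bivalent vaccine was launched. For most of the vaccination campaign the two cannot both hold, and the only other printed category, never vaccinated, is false for these people.

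Applied as written, the matched comparison would lose booster recipients, the group for whom both vaccines were first authorised. It would keep never-vaccinated recipients and the unusual recipients whose preceding dose came after bivalent launch. Because time zero is the first bivalent dose (Section 9.1.1.2), that preceding dose would have to be a different COVID-19 vaccine. Section 9.9 describes the cohort estimate as the effect in the vaccinated; this subset would not represent them. Precision would suffer too. In Table 3, at a true risk ratio of 2 and a risk of 1 per 50,000, going from 1,000,000 to 100,000 per group widens the interval from 1.17–3.42 to 0.37–10.92.

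**Working it through.** The protocol gives no figure of its own on this point, so the check is calendar arithmetic.

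**Inputs.** First allowed j: September 2022 (9.1.1.3 with 9.2.3, best case). Bivalent doses: 1 September 2022 to 31 August 2023, 365 days (9.2.3, Section 5). Minimum gaps: 11 and 5 months (9.2.1.1); 3 months, the authorised minimum in Section 7, for comparison.

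**Condition.** A recipient has a category only if the last dose is on or after 1 September 2022 and no later than the bivalent date minus the gap. The earliest bivalent date with a category is therefore 1 September 2022 plus the gap. The latest usable last dose is 31 August 2023 minus the gap.

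| Gap | First bivalent date with a category | Days with none | Usable months j |
|---|---|---|---|
| 11 months | 1 August 2023 | 334 of 365 | September 2022 only |
| 5 months | 1 February 2023 | 153 of 365 | September 2022 to March 2023 (7) |
| 3 months | 1 December 2022 | 91 of 365 | September 2022 to May 2023 (9) |

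These dates do not depend on uptake. A national launch after 1 September 2022 moves them later. The 3-month row shows that the slip would leave the first three months empty even without the longer gaps.

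**Share of people (assumptions, not protocol data).** Let T be the months from 1 September 2022 to the bivalent dose and G the gap. A recipient has no category when T < G. With T uniform on 0–12, the share is E[min(G, 12)]/12. At the minimum gap this is 11/12 = 92% and 5/12 = 42%. With G uniform on 5–8 it is 6.5/12 = 54%; on 11–12, 11.5/12 = 96%. Other patterns, with G uniform over the range shown:

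| Assumed uptake | G 11–12 | G 11–18 | G 5–6 | G 5–8 | G 5–12 | G 5–18 |
|---|---|---|---|---|---|---|
| Even over 12 months | 96% | 99% | 46% | 54% | 71% | 84% |
| Half in Sept–Dec 2022, half in Jan–Aug 2023 | 97% | >99% | 59% | 66% | 78% | 88% |
| All in Sept–Dec 2022 | 100% | 100% | 100% | 100% | 100% | 100% |
| All in Mar–Aug 2023 | 92% | 99% | 0% | 11% | 43% | 69% |

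If j may start at the first month of COVID-19 vaccination, the share is 0% in every row.

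**Connective.** B and C exclude each other, so requiring A, B and C together admits nobody. If any one suffices, A alone admits any gap and the month limits have no force for people who meet A. Only A AND (B OR C) gives a non-empty cohort in which the limits apply.

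**The case against.** The best defence is that nobody would apply the range literally. A recorded dose in January 2022 is complete information on the matching variable, and nothing says that a month outside the parenthesis is dropped. The research question (8.1) speaks of comparable vaccination history, and the subgroups in 9.3.5 presuppose matching on earlier doses. This stands as evidence of intent, and j was probably meant to span the whole vaccination programme. It does not make the printed rule right: the categories are listed, matching is exact, and no category holds an earlier dose. The remark in 9.1.1.3 about tailoring concerns which variables a data source holds, not the range of j.

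A reader might infer more than the documents support:

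- *That the missing connective yields different cohorts at different sites, or an empty one.* Section 9.6.3 has the programs developed and tested centrally and then sent to the data access providers, so sites do not each interpret the rule. B and C are evidently two branches of one rule, and the list's nesting in the laid-out document may make that plainer.
- *That an old primary series satisfies the gap despite a recent booster.* The wording is loose, but the same conditions refer to the interval between doses, which points to the latest dose.
- *That 11 and 5 months contradict local policy.* The protocol quotes no national interval. Three months is an authorised minimum, and the three-month rule for the self-controlled design (9.2.1.2) serves a secondary analysis. Common cut-offs applied to both pair members mainly restrict the population; no bias is shown.
- *That most booster recipients are lost for certain.* The calendar settles this only for vaccination months under the 11-month rule. The 5-month share runs from 0% to 100% across the assumed patterns.

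**Conclusion.** The range of j in Section 9.1.1.3 is stated wrongly and should be corrected. As printed, with a September 2022 launch and bivalent use ending by August 2023, eligible booster recipients have no category in 11 of the 12 vaccination months under the 11-month rule and in 5 of 12 under the 5-month rule. That removes nearly all of the vaccination window for the first group and an uptake-dependent share of the second from the primary matched comparison. The dates rest only on the protocol's text, with gaps counted to the last dose and the sub-conditions read as A AND (B OR C). The percentages of people rest on assumed uptake and gaps. The connective and the reference to prior vaccination are minor points of wording. The protocol does not show that its cut-offs are wrong, only that it gives no reason for them.

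**What to change.** In Section 9.1.1.3, let j range from the first month of COVID-19 vaccination in each country to the month of time zero. This changes one phrase and needs no new data, since the same vaccination records already supply the dose count.

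As a minor clarification in Section 9.2.1.1, print the sub-conditions as A AND (B OR C) and refer to the last COVID-19 vaccine dose. This changes wording only.

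Optional: give a reason for the common 11- and 5-month cut-offs, or replace them with locally recommended intervals. Replacement costs more: a dated table of recommendations, which the protocol does not contain, with at least two intervals per country or region, and more varied gaps across data sources.
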